Obtain PK samples			X m	X n					X n	X m	X n	

Day a	−28 to −2	-1	1	2	3	4	5	6	7	8/ET	9	36 (+7 days)
	Screening											FU Contact b
												(EOS)
Review and record prior and concomitant medications	X°	X	X	X	X	X	X	X	X	X	X	
Assess for AEs and SAEs	X	X	X	X	X	X	X	X	X	X	X	X
CCI		X										

Abbreviations: →= ongoing/continuous event; AD=atopic dermatitis; CRU=clinical research unit; ISGA=investigator's static global assessment; %BSA=percent of body surface area; ECG=electrocardiogram; EOS=End of Study; ET=Early Termination; FSH=follicle-stimulating hormone; FU= Follow-up; HIV=human immunodeficiency virus; HepBsAg=hepatitis B surface antigen; HepBcAb=hepatitis B core antibody; HCVAb=hepatitis C antibody; PK=pharmacokinetic; AE=adverse event; SAE=serious adverse event;

- a. Day relative to start of study treatment (Day 1).
- b. Follow-up contact will be completed on Day 36 (28 +7 calendar days after the last application of the investigational product) to capture any potential adverse events and to confirm appropriate contraception usage.
- c. Subjects will be admitted to the Clinical Research Unit (CRU) on Day -1.
- d. Subjects will discharge from CRU on Day 9 after completion of all assessment on Day 9.
- e. A physical examination will be conducted at ET.
- f. A skin examination will be conducted by dermatologist.
- g. Treatable percent body surface area (%BSA) is defined as the percent of a subject's total body surface area that is AD-involved, excluding the scalp and venous access areas.
- h. Only weight will be measured on Day 1.
- i. Vital signs (pulse rate and blood pressure) taken supine position after subject has been calmly lying face up for 5 minutes.
- j. ECG will be collected in single.
- k. Any female subject who has been amenorrheic for at least 12 consecutive months.
- 1. Day -1 urine drug testing does not have to be repeated if urine drug testing is completed within 7 days prior to Day -1.
- m. Obtain PK samples at predose, 3 hours and 12 hours post Day 1 and Day 8 AM dose.
- n. Obtain PK samples prior to AM dose on Day 2 and Day 7 (at 24 hours post Day 1 and Day 6 AM dose). Obtain PK samples on Day 9 at 24 hours post Day 8 AM dose.
- o. All medications and non-medication therapies used within 28 days prior to Screening.
- p. If not collected on the designated collection day, collect at the next available time point when CCI in conjunction with a subject visit.

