- An additional Phase 3, multicenter, open-label, long-term extension study of crisaborole ointment 2% for the treatment of mild to moderate AD in adults and children as young as 2 years of age evaluated the long-term safety of topical crisaborole (Study AN2728-AD-303). Crisaborole showed an acceptable safety profile for long-term topical treatment of mild to moderate AD in adults and children as young as 2 years of age.

Crisaborole has been well tolerated across completed clinical studies. No clinically important safety signals have been identified, including during a Phase 3 multicenter, open-label, long-term extension study of crisaborole ointment 2% for mild to moderate AD in adults and children as young as 2 years of age. Most AEs have been mild, and most considered unrelated or unlikely to be related to investigational product. The most common drug-related AEs have been application site reactions.

In a thorough QT (TQT) study (Study AN2728TQT108) in which healthy subjects were treated with crisaborole ointment 2% at a therapeutic dose (15 g, representing 30% BSA treatment) or a supratherapeutic dose (45 g, representing 60% BSA treatment), mean  $C_{max}$  values of 36.9 ng/mL and 87.4 ng/mL were observed in therapeutic and supratherapeutic dose groups, respectively, at Day 9. At both therapeutic and supratherapeutic doses had no effect on cardiac repolarization based on results from the primary assessment and the pharmacokinetic-pharmacodynamic analysis.

Additional information for this compound may be found in the single reference safety document (SRSD), which for this study is current version of the crisaborole IB.

[figure not shown]

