### 2. STUDY OBJECTIVES AND ENDPOINTS

Primary Objective for Cohort 1	Primary Endpoint for Cohort 1				
To investigate the skin irritation potential of a single topical dose of crisaborole ointment 2% and vehicle in adult Japanese healthy subjects	Skin irritation index a				
Secondary Objective for Cohort 1	Secondary Endpoint for Cohort 1				
To investigate the safety and tolerability of a single topical dose of crisaborole ointment 2% and vehicle in adult Japanese healthy subjects	Assessment of adverse events (AEs)				
Primary Objective for Cohort 2	Primary Endpoint for Cohort 2				
To investigate the safety and tolerability of multiple topical doses of crisaborole ointment 2% BID in adult Japanese subjects with mild to moderate AD	Assessment of AEs, clinical laboratory tests, vital signs, and 12 lead electrocardiogram (ECG)				
Secondary Objective for Cohort 2	Secondary Endpoint for Cohort 2				
To characterize plasma PK of crisaborole and its identified main oxidative metabolites (AN7602 and AN8323) following multiple topical doses of crisaborole ointment 2% BID in adult Japanese subjects with mild to moderate AD	• PK parameters: $C_{max}$ , $T_{max}$ , $AUC_{last}$ , $AUC_{24}$ , $AUC_{\tau}$ on Day 1 and Day 8, and $R_{ac}$ ( $C_{max}$ ) and $R_{ac}$ ( $AUC_{\tau}$ ) on Day 8				
CCI	• CCI				

Abbreviations: AD=atopic dermatitis; AE=adverse event;  $C_{max}$ =maximum observed plasma concentration; AUC $_{\tau}$ = area under the plasma concentration-time profile from time zero to time tau ( $\tau$ ), the dosing interval, where  $\tau$  = 12 hours for BID dosing; BID=twice daily; AUC $_{last}$ = area under the plasma concentration-time curve from zero time until the last measurable concentration ( $C_{last}$ ); AUC $_{24}$ = area under the plasma concentration-time curve from time zero to the 24 hours postdose;  $T_{max}$ =time to reach maximum observed plasma concentration; ECG=electrocardiogram; PK=pharmacokinetics.

a: Skin irritation index is calculated as the sum of the individual maximum irritation scores divided by the number of subjects and multiplied by 100, which ranges from 0 to 400.

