### 5.7.2.1. Study Treatment Regimen

From Day 1 AM through the Day 8 AM dose, all applications of the investigational product will be dispensed and applied by study site staff. The subject-specific per application dose will be applied BID to all treatable AD-involved areas identified on Day 1 except on Days 1 and 8, when investigational product will be administered QD in the AM. Every effort must be made for the AM dose applications on Days 2–8 to be completed at 24 ±1 hour intervals from the recorded time of completion of the Day 1 dose application, for each subject. The PM dose applications on Days 2–7 will be applied at 12 ±1 hour after the recorded time of completion of the each AM dose application, for each subject.

The per application dose will be calculated using the formula provided below in Section 5.7.2.4, based on each subject's total BSA in square meters (Section 5.7.2.2) and Treatable %BSA (Section 5.7.2.3) on Day 1. The intended dose of the investigational product application to the treatable AD-involved areas is approximately 3 mg/cm². The investigational product should be applied evenly to all treatable areas. The per application dose will be expressed as the weight of ointment in grams. The per application dose will remain fixed and the investigational product will be applied to all treatable AD-involved areas identified on Day 1, regardless of whether they become clinically clear. Any AD-involved venous access areas and/or new AD lesions that appear after Baseline may be treated only with bland emollients until discharge from CRU on Day 9.

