- **PM application:** wearing gloves, study site staff will apply the calculated amount of study drug (per application dose) to all treatable AD lesions identified on Day 1;
- Assess symptoms by spontaneous reporting of AEs and by asking the subjects to respond to a nonleading question such as "How do you feel?"

## 6.2.2.4. Day 3 to 6

The following procedures will be completed:

- Review and record concomitant medications;
- AM application: wearing gloves, study site staff will apply the calculated amount of study drug (per application dose) to all treatable AD lesions identified on Day 1;
- **PM application:** wearing gloves, study site staff will apply the calculated amount of study drug (per application dose) to all treatable AD lesions identified on Day 1;
- Assess symptoms by spontaneous reporting of AEs and by asking the subjects to respond to a nonleading question such as "How do you feel?"

## 6.2.2.5. Day 7

The following procedures will be completed:

- Collect blood samples for PK analysis at 24 hours following application on Day 6 AM;
- Review and record concomitant medications;
- AM application: wearing gloves, study site staff will apply the calculated amount of study drug (per application dose) to all treatable AD lesions identified on Day 1;
- **PM application:** wearing gloves, study site staff will apply the calculated amount of study drug (per application dose) to all treatable AD lesions identified on Day 1;
- Assess symptoms by spontaneous reporting of AEs and by asking the subjects to respond to a nonleading question such as "How do you feel?"

# 6.2.2.6. Day 8

- Review and record concomitant medications.
- Collect single 12-lead ECG measurements prior to insertion of the IV catheter.

- Collect supine BP and PR prior to insertion of the IV catheter.
- Obtain blood and urine samples for safety laboratory tests.
- Collect a blood sample for PK analysis at predose.
- AM application: wearing gloves, study site staff will apply the calculated amount of study drug (per application dose) to all treatable AD lesions identified on Day 1.
- Collect blood samples for PK analysis at 3 and 12 hours following application on Day 8.
- Assess symptoms by spontaneous reporting of AEs and by asking the subjects to respond to a nonleading question such as "How do you feel?"

# 6.2.2.7. Day 9

- Review and record concomitant medications.
- Collect blood samples for PK analysis at 24 hours following application on Day 8.

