#### 6.1.4. Vital Signs

Vital signs data are one of the primary endpoints for Cohort 2. The analysis of vital signs data will be based on the safety analysis population. Absolute values and changes from

baseline in blood pressure and pulse rate will be summarized and listed by treatment and visit in accordance with the Pfizer data standards. Baseline will be the last predose measurement.

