## 6.1.5. Electrocardiogram

ECG data are one of the primary endpoints for Cohort 2. Absolute values and changes from baseline for the ECG parameters, QT interval, heart rate, QTc (ie, QTcF) interval, PR interval, QRS interval, and RR interval will be summarized descriptively by treatment and visit for the safety analysis population.

The number (%) of subjects with maximum postdose QTc values and maximum increases from baseline in the following categories will be tabulated by treatment:

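### Does taking the Cohort 2 Day 8 ECG and vital signs before that day's application undermine the SAP's baseline rule and its postdose QTc table?

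*Protocol*

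**What the plan says.** The Cohort 2 Schedule of Activities places ECG and vital signs at Screening, Day 1 and Day 8/ET. Protocol 6.2.2.2 lists the Day 1 readings among the procedures done before dosing. Protocol 6.2.2.6, for Day 8, has no such subheading. Its list runs: "Collect single 12-lead ECG measurements prior to insertion of the IV catheter", then supine blood pressure and pulse, the safety laboratory samples, "Collect a blood sample for PK analysis at predose", and only then the morning application. Schedule footnote m uses the same term for PK sampling on both days: "Obtain PK samples at predose, 3 hours and 12 hours post Day 1 and Day 8 AM dose". Under Protocol 5.7.2.1 the evening application "will be applied at 12 ±1 hour after the recorded time of completion of the each AM dose application".

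SAP 6.1.3 (laboratory data) and 6.1.4 (vital signs) each state "Baseline will be the last predose measurement". SAP 6.1.5 (ECG) has no such sentence. It tabulates "The number (%) of subjects with maximum postdose QTc values and maximum increases from baseline" by category, and Protocol 9.5.1 also uses *postdose*. Protocol Section 2 makes laboratory tests, vital signs and ECG part of the Cohort 2 primary endpoint, together with adverse events.

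**The concern.** The protocol calls the point just before the Day 8 morning application *predose*. If the SAP uses the word in the same way, the last predose vital-signs and laboratory values are the Day 8 values themselves, and change from baseline is zero for every completer. A table of maximum postdose QTc would have no scheduled data, because no ECG follows an application on the same day. ECG also has no stated baseline.

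Apart from programming, a table with that title from a maximal-use cohort might be read as covering the hours around peak concentration. The earlier paediatric maximal-use study had a mean Day 8 crisaborole Cmax of 127 ng/mL. In the thorough QT study, mean Cmax "values of 36.9 ng/mL and 87.4 ng/mL were observed in therapeutic and supratherapeutic dose groups" respectively, so the maximal-use mean is 127 / 87.4 = 1.45 times the supratherapeutic one. A reader looking for reassurance at peak would not find it in this table.

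**Working it through.** **1. Schedule.** Scheduled ECG and vital-signs readings per completer: 3 (Screening, Day 1, Day 8). On treatment: 1. After an application on the same day: 0. Applications before the Day 8 morning dose: 1 (Day 1) + 6 × 2 (Days 2–7) = 13, of 14 in all.

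**2. Time since the last application (Protocol 5.7.2.1).** Measured from the Day 1 application, Day 7 morning is at 144 ± 1 h. Day 7 evening is 12 ± 1 h later, so 154 to 158 h. Day 8 morning is at 168 ± 1 h. The gap is nominally 12 h, with limits 167 − 158 = 9 h and 169 − 154 = 15 h. The reading itself precedes the morning application by an unstated time. Median crisaborole Tmax in the earlier study was 3 h.

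**3. Illustrative level at that time.** Inputs are the Day 8 means in Protocol Table 1. Assume steady state (C0 = C12 = c), sampling at 0, 3 and 12 h, and C3 = f × Cmax.

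- Linear rule: 6 × (C3 + c) = AUC12.
- Linear/log rule: 1.5 × (c + C3) + 9 × (C3 − c) / ln(C3/c) = AUC12.
- Crisaborole, f = 1, linear: c = (949 − 6 × 127) / 6 = 31.2 ng/mL. Linear/log: 42.5.
- Crisaborole, f = 0.85, linear: c = (949 − 6 × 107.95) / 6 = 50.2. Linear/log: 54.7.

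| Analyte | Mean Cmax | f assumed | c (ng/mL) | c / Cmax |
|---|---|---|---|---|
| Crisaborole | 127 | 0.85–1.00 | 31.2–54.7 | 25–43% |
| AN7602 | 40.8 | 0.85–1.00 | 7.5–15.6 | 18–38% |
| AN8323 | 6150 | 0.90–1.00 | 4417–5038 | 72–82% |

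For AN8323, f = 0.85 gives c above C3 and is not used. Near trough is therefore a fair description for crisaborole and AN7602, but not for AN8323. The crisaborole value is 31.2 / 87.4 = 36% to 54.7 / 87.4 = 63% of the QT study's supratherapeutic mean Cmax. These figures treat paediatric means as one profile, although the SD of Cmax is 196 and N is printed as 23 in the table header but 32 and 33 in its footnotes. They show scale only.

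**4. Which baseline the rule selects.** There are two candidate readings.

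- *PK-sampling sense.* Day 8 change = Day 8 − Day 8 = 0 for every completer. SAP 6.1.4 asks for changes from baseline by treatment and visit, so this reading makes the section pointless.
- *Before the first application.* Baseline is Day 1 for vital signs and Day −1 for laboratory data. *Last* then has a clear job: it chooses these over Screening.

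Other text supports the second reading. SAP Appendix 1 gives the Day 1 visit a target before the start of study treatment, and puts everything from Day 2 onwards in the Day 8/ET window. Protocol 5.7.2.1, 5.7.2.4 and 5.10.1 use *Baseline* for Day 1. The SAP never applies *predose* to Day 8; its PK section (6.2.2) calls the Day 7, 8 and 9 concentrations troughs.

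**5. ECG baseline.** Only Screening and Day 1 precede treatment. SAP 6.6 treats screening ECGs used for eligibility as source data that need not be reported. The Day 1 pre-application ECG remains, and it falls in the Appendix 1 Day 1 window.

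**6. Postdose.** A reading after 13 applications is after dosing. With Day 1 as baseline, the QTc category table is filled by the Day 8/ET ECG plus any triggered or unscheduled repeats under Protocol 7.1.5.

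**The case for a change.** The best case for an edit is that these are primary-endpoint measures and the text should not depend on inference. Appendix 1 governs safety summaries shown by visit, while the QTc category table is by treatment. The windows label visits and do not define baseline. The pretreatment laboratory sample is on Day −1, yet the window is labelled Day 1. SAP version 2.0 was issued to clarify 6.1.4 and 6.1.5 and left these points open. The edit would be cheap.

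Part of this stands. The Day 8 timing comes from list order and from the rule in Protocol 6.2 that puts ECG and vital signs ahead of blood draws; it is not stated outright. SAP 6.1.5 does omit a baseline, and *postdose* is loose. But a loose phrase matters only if it leaves two workable analyses, and here only one is workable. The alternative gives zero changes and an empty QTc table, which any programmer would recognise as a misreading. The worry about a misleading title is also hypothetical: neither document presents the Day 8 ECG as evidence at maximal-use peak.

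**Conclusion.** No change is needed. The schedule is as described, and anyone citing the Day 8 ECG or vital signs should know that they are end-of-interval readings for crisaborole and AN7602. As a design this is coherent: a pre-application reading on Day 1 is compared with a pre-application reading after 13 applications, in a descriptive study with 10 active and 2 vehicle subjects and no hypothesis test. Acute cardiac safety has separate support in the thorough QT study and in the 215-fold nonclinical margin in Protocol 1.3.1, which is based on maximal-use exposure.

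The SAP wording is a gap that analysts will fill correctly. Spelling out the baseline and the meaning of *postdose* would alter no reading, no derived change and no table count, so the effect on results is nil. This rests on two assumptions: that Day 8 procedures follow the listed order, and that baseline means the last value before the first application, as Appendix 1 and the protocol's use of the term indicate. The trough percentages depend on the assumed C3 fraction and on paediatric means, and the conclusion does not depend on them.

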# 1.3.2. Pharmacokinetics (PK)

The efficacy of crisaborole for the treatment of AD is not dependent on systemic exposure. The development program evaluated systemic exposure to crisaborole and its main metabolites relative to establishing the safety of topically applied crisaborole. Clinical studies in healthy adult volunteers, in pediatric and adolescent subjects with AD, and in adults with psoriasis demonstrated similar PK profiles and systemic exposure, irrespective of underlying disease or age, and establish that following topical application, crisaborole penetrated through the stratum corneum, epidermis, and dermis of human skin, as evidenced by the presence of crisaborole and its main metabolites in plasma. Upon reaching the systemic circulation, biotransformation of crisaborole is rapid and extensive and primarily consists of oxidative deboronation/hydrolysis to produce AN7602 by CYP3A4 and CYP1A1/2, followed by subsequent downstream oxidation of this metabolite to form AN8323, without notable species-related qualitative differences. These two main metabolites of crisaborole observed in plasma following topical application to several species, including humans, were found to be inactive against PDE-4. Further, as a result of rapid biotransformation, systemic exposure of crisaborole is limited following topical application of crisaborole.

In the clinical PK study conducted under maximal use conditions (maximal use systemic exposure [MUSE] study) in children and adolescents aged 2-17 years with extensive AD (mean treatable percent body surface area [Treatable %BSA] 48.7%; range 27%-92%), absorption across the skin was rapid, with a median of time to reach maximum observed concentration ( $T_{max}$ ) of 3.0 hours on both Day 1 and Day 8 (Study AN2728-AD-102). Steady state was achieved within the first 8 days of dosing, with a mean crisaborole of maximum observed concentration ( $C_{max}$ ) of 127 ng/mL. Minimal plasma accumulation of crisaborole and AN7602 was observed at steady state whereas AN8323 displayed an approximately 3-4-fold accumulation based on Cmax and area under the concentration-time curve from time zero to the 12 hours (AUC12).

Table 1. Key Pharmacokinetic Parameters in AD Subjects (2–17 years) (AN2728-AD-102)

Analyte	Study Day	Mean Parameter (SD) (N = 23)							
		C max (ng/mL)	T max (median [range]) (h)	AUC 12 (ng·h/mL)					
Crisaborole	Day 1	111 (113)	3.00 (3.00–12.0)	759 a (730)					

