### 1.4. Rationale

# 1.4.1. Study Rationale

This Phase 1 study is planned to evaluate the skin irritation potential of crisaborole ointment 2% and vehicle in healthy adult male Japanese subjects in Cohort 1, and safety and PK of crisaborole ointment 2% in adult Japanese subjects with AD in Cohort 2.

There have been reports about racial difference in skin pathophysiology,  and conflicting literatures about the racial difference in irritant response with topical therapy.  Even though there was no evidence of cutaneous sensitization in the RIPT study, and the cutaneous irritation was very minimal in Western subjects (Section 1.3.3), it is considered useful to evaluate the irritant response in Japanese subjects. All subjects in Cohort 1 will be treated topically under occlusive patch conditions with 2 study products (crisaborole ointment 2% and vehicle) on the infrascapular area of the back for 48-hour duration before irritant response assessment. The assessment will be based on the Japan standard evaluation methods.  The cohort will be conducted as an observer-blinded design to minimize evaluation bias for skin irritation.

Cohort 2 will be conducted in adult Japanese subjects with mild to moderate AD with Treatable %BSA >25%. This cohort will investigate the safety and PK of crisaborole ointment 2% in Japanese subjects with AD under MUSE condition. The Cohort 2 can provide useful information to evaluate the safety and possible maximum systemic exposure of crisaborole ointment 2% in Japanese subjects under the maximal use condition to enable further development in Japan. The cohort will be conducted as a double-blind design to minimize evaluation bias for safety. Considering the well acceptable safety results in previous MUSE study, the two Phase 3 and one long-term safety studies, and the securement of safety by confinement, the Cohort 2 can be conducted in parallel with Cohort 1 study.

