# 6.2. Study Period

For the study period described below, when multiple procedures are scheduled at the same time point(s) relative to dosing, the following chronology of events should be adhered to, where possible.

- ECGs: obtain prior to vital sign measurements, but prior to blood specimen collection;
- BP/PR: obtain prior to blood specimen collection;
- PK blood specimens: obtain at the scheduled time;
- Other procedures: may be obtained before or after blood specimen collection.

When an IV catheter is utilized for blood sample collections, ECGs and vital sign assessments (PR, BP) should be collected prior to the insertion of the catheter.

#### 6.2.1. Cohort 1

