# 6.2.2.1. Day -1

Subjects will be admitted to the CRU at least the day prior to Day 1 dosing. The following procedures will be completed following admission to the CRU:

- Review inclusion and exclusion criteria;
- Obtain blood and urine samples for safety laboratory tests. The results must have no clinically significant findings, as judged by the investigator, in order for a subject to be given investigational product on Day 1;
- Collect urine for drug testing. Do not have to be repeated if urine drug testing is completed within 7 days prior to Day –1;
- Collect urine pregnancy test for female subjects of childbearing potential;
- Confirm highly effective contraception is being used for female subjects of childbearing potential;
- CC
- Assess baseline symptoms/AEs;
- Review changes in the subject's medical history, including medication history since screening;
- Conduct physical examination except skin examination.

# 6.2.2.2. Day 1

**Prior to dosing**, the following procedures will be completed:

- Review inclusion and exclusion criteria;
- Conduct physical examination for skin examination;
- Complete the ISGA (the ISGA score must be 2 or 3 on Day 1 for subject to be eligible);
- Record treatable AD areas;
- Calculate and record Treatable %BSA;
- Assess baseline symptoms/AEs;
- Collect weight;
- Collect 12-lead ECG measurements prior to insertion of the IV catheter;
- Collect supine BP and PR prior to insertion of the IV catheter;
- Collect a blood sample for PK analysis at predose;
- Review and record prior medications;
- After all predose procedures have been completed, apply the investigational product (see the Administration section);
- AM application: wearing gloves, study site staff will apply the calculated amount of study drug (per application dose) to all treatable AD lesions identified on Day 1;
- Collect blood samples for PK analysis at 3 and 12 hours following application on Day 1;
- Assess symptoms by spontaneous reporting of AEs and by asking the subjects to respond to a nonleading question such as "How do you feel?"

# 6.2.2.3. Day 2

The following procedures will be completed:

- Collect blood samples for PK analysis at 24 hours following application on Day 1;
- Review and record concomitant medications:

- AM application: wearing gloves, study site staff will apply the calculated amount of study drug (per application dose) to all treatable AD lesions identified on Day 1;

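### Does Cohort 2 need an ECG and blood pressure reading near the expected crisaborole peak on Day 8?

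*Protocol*

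**What the plan says.** The Cohort 2 Schedule of Activities marks ECG and vital signs at Screening, Day 1 and Day 8/ET only. On Day 1 both sit under a heading for procedures before dosing (Protocol 6.2.2.2: "Collect 12-lead ECG measurements prior to insertion of the IV catheter"), so they are baseline. The Day 8 list in 6.2.2.6 has no such heading. It says "Collect single 12-lead ECG measurements prior to insertion of the IV catheter", gives the same instruction for blood pressure and pulse rate, and then lists safety laboratory samples, the predose PK sample and the morning application. After the application come "Collect blood samples for PK analysis at 3 and 12 hours following application on Day 8" and adverse event questioning. Day 9 has neither ECG nor vital signs.

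The Schedule gives clock times for PK ("Obtain PK samples at predose, 3 hours and 12 hours post Day 1 and Day 8 AM dose"), but its footnotes for ECG and vital signs cover only the number of readings and posture. Protocol 6.2 adds that, where a catheter is used, "ECGs and vital sign assessments (PR, BP) should be collected prior to the insertion of the catheter". Section 7.1.5 refers back to the study procedures for ECG times.

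SAP 6.1.4 and 6.1.5 summarise these data by treatment and visit. SAP 6.1.5 also tabulates the maximum QTc after dosing.

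**The concern.** Protocol 1.3.2 reports a median crisaborole Tmax "of 3.0 hours on both Day 1 and Day 8" in the paediatric maximal-use study. Protocol 1.4.1 says Cohort 2 is to inform on safety and on "possible maximum systemic exposure of crisaborole ointment 2% in Japanese subjects under the maximal use condition". If the only post-baseline ECG and blood pressure reading comes just before a dose, two primary safety endpoints are measured when crisaborole is probably near its lowest level of the dosing interval. A short-lived effect at peak could be missed, although staff already see the subject at 3 hours to draw blood. The SAP's maximum QTc after dosing would then be a single, probably near-trough value for a completer with no unscheduled ECG.

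Because the time is not written down, a site could in principle take the reading later, and time since dose could differ between subjects.

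**Working it through.** **When the Day 8 reading falls.** Protocol 5.7.2.1 puts morning doses at 24 ± 1 hour intervals and the evening dose at 12 ± 1 hour "after the recorded time of completion of the each AM dose application". The gap from the Day 7 evening dose to the Day 8 morning dose is nominally 24 − 12 = 12 h. If consecutive morning doses are 24 ± 1 h apart, it runs from 23 − 13 = 10 h to 25 − 11 = 14 h. If each morning dose is instead held within 1 h of the Day 1 clock time, it runs from 9 to 15 h. A reading just before the Day 8 application is therefore nominally 12 − 3 = 9 h past the median peak.

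**What it still captures.** By then a completer has had 1 (Day 1) + 6 × 2 (Days 2 to 7) = 13 applications. The reading is thus after dosing in the ordinary sense of comparison with a Day 1 baseline, and the SAP's wording can be applied to it.

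**How far below peak (illustration only).** Inputs are Day 8 means from Protocol Table 1: crisaborole Cmax 127 ng/mL and AUC12 949 ng·h/mL. Assume steady state, with concentration x at 0 and 12 h and c at 3 h.

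- Linear rule: 1.5(x + c) + 4.5(c + x) = 6(x + c) = 949.
- Linear up, log down: 1.5(x + c) + 9(c − x)/ln(c/x) = 949.

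| Assumed c (ng/mL) | x, linear | x/c | x, log down | x/c |
|---|---|---|---|---|
| 127 | 31.2 | 24.5% | 42.5 | 33.5% |
| 110 | 48.2 | 43.8% | 53.3 | 48.4% |
| 100 | 58.2 | 58.2% | 60.6 | 60.6% |

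The values 110 and 100 are assumptions. The first row is the extreme case. Mean Cmax averages individual maxima whose Tmax ranged from 3 to 24 h, so the mean 3-hour concentration cannot exceed 127. The inputs are also noisy (Cmax SD 196, AUC12 SD 1,240), and the table's header N of 23 disagrees with its footnotes (32 and 33). For AN8323 the linear rule gives 63,400/6 − 6,150 = 4,417, or 71.8% of Cmax, so that metabolite is largely represented before the dose.

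**What a 3-hour reading would bring.** It would add 12 ECGs and 12 blood pressure and pulse sets, one per subject.

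- *Clock time.* Day 1 baseline and Day 8 predose readings fall at about the same hour. A 3-hour reading does not, so its change from baseline mixes drug effect with time of day, and only two vehicle subjects are available to separate them.
- *Treated skin.* Subjects have at least 25% of body surface treated. Protocol 4.4.2 and 5.7.2.6 bar washing treated areas within 4 hours of application and warn against wiping ointment off or occluding it. A 3-hour reading falls inside that period. Where electrode or cuff sites are treated, it could disturb ointment just before the 3-hour PK sample, which feeds a secondary endpoint.
- *Knock-on rules.* It needs an exception to the catheter rule in 6.2. It comes under the repeat-ECG procedure in 7.1.5. Taking the larger of two readings raises each subject's maximum slightly by chance. The SAP Appendix 1 tie rule, if applied to two Day 8 readings, would keep only the later one in by-visit summaries; that problem arises only if a second reading is added.

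**The case for a change.** The best case for a change is that the gap is real and cheap to close. ECG and vital signs are primary endpoints, the subjects are confined, staff attend at 3 hours anyway, and Protocol 7.1.4 already permits extra blood pressure times. Keeping the predose reading as well would preserve one clock-matched comparison. Earlier cardiac data do not fully cover the exposure either: the highest mean Cmax in the thorough-QT study was 87.4 ng/mL, and 87.4/127 = 0.69 of the paediatric maximal-use mean.

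Much of this stands. The Day 8 time is not written down, and followed as listed, the plan has no scheduled post-baseline reading near 3 hours. A sponsor could reasonably have chosen to add one.

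It does not show that the present choice is wrong. Protocol 1.4.1 names safety and possible maximum exposure as two things to learn under maximal-use conditions, and Section 2 gives them separate objectives. Neither section sets out to relate ECG to peak concentration. The thorough-QT study was negative on both its primary and its concentration-response analysis (Section 1.3.4). Section 1.3.1 gives a 215-fold margin for acute effects such as cardiovascular ones, calculated from exposure in the paediatric maximal-use study. The 69% figure sets healthy subjects against patients aged 2 to 17 with extensive disease, so it is only a rough guide to adults here. Adverse events are assessed every day.

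**Conclusion.** No change is needed. The unstated time is a gap that staff and analysts fill sensibly. List order, the catheter rule and the predose blood sample all point to a reading before the Day 8 application, and the report can describe it as such. A label in 6.2.2.6 would tidy the text without altering a result.

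The absence of a 3-hour reading is a fair trade-off. The plan gives up a look near the median crisaborole peak. In return it keeps readings clock-matched to baseline, taken before any catheter and without disturbing ointment ahead of the PK sample. The protocol does not state these as its reasons; they follow from its other rules.

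The size is modest: one reading per subject, at an illustrative 25% to 61% of the 3-hour crisaborole level, in a descriptive cohort of 12 with no hypothesis test. This rests on predose timing being followed, on subjects completing treatment (an early-termination reading can fall at any time since dose), and on paediatric means carrying over to Japanese adults. The Day 8 ECG and vital sign results should be read as effects after a week of treatment at probably near-trough exposure, not as evidence about the peak.
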